## 10.5 Data and Safety Monitoring

### 10.5.1 Interim Monitoring Guidelines

This study will be formally monitored at least annually by an ACTG-appointed SMC (via the standing committee for the ARTS TSG). The first interim review will occur no more than one year after the enrollment of the first participant or 3 months after 25 women have completed the study, whichever occurs earlier. An additional SMC review may be triggered if the accrual at one year is less than 50% of total expected accrual (e.g., fewer than 58 of 116 women across all 4 arms). This additional review, under the contingency of very slow accrual, would provide an opportunity for the SMC to review the available estimate of coefficient of variation of the AUC of LNG(0-8hrs) in order to see if the calculated CV varies greatly from the CV estimate used above to support the study size/design. Due to the two-stage testing workflow to achieve PK parameter estimates from blood samples, and the desire not to increase the study budget by requiring expedited shipping or testing, the timeframe for this additional review could be 6 months or longer.

Outside of this additional review contingency plan, there are no plans to initiate PK testing prior to completion of a primary objective, and thus no planned early looks at the primary efficacy outcome.

An unplanned interim review will be triggered if, at any time, any participant experiences an SAE that is attributed to LNG (by adjudication by the core team and DAIDS clinical representative), or if more than five women need to be replaced (as per the guidelines for replacement as described in [section 9.2](#)) in the overall study sample. An SMC review can also be requested at any time at the request of the team or sponsor.

**Note:** Eligibility and enrollment issues that cause participant replacement will not be included as an SMC trigger. The participant replacement interim review trigger will be determined based strictly on criteria stated in [section 9.2 \(Premature Study Discontinuation\)](#) of the protocol.

Any/all SMC reviews will include administrative/trial conduct data as well as safety data according to the safety-related outcomes enumerated above.

Routine monitoring reports are distributed to core team and are detailed in the study monitoring plan (SMP): screening, accrual, data delinquency, study status, data and sample completeness, with attention to intensive PK sampling for the primary efficacy outcome. The routine safety monitoring report is distributed to the DAIDS Clinical Representative and a subset of the core team (to include the study chairs) every 3 months.

Further details about monitoring of this study are available in the SMP.

## 10.6 Analyses

If accrual to study groups is such that one primary objective is able to be addressed before the other due to unequal accrual rates, then the team will plan to perform final analyses that include completely accrued groups, even if accrual is still occurring to groups required for the other primary objective. This is because it is anticipated that each primary objective can be published independently.

### 10.6.1 Primary Efficacy Analysis

The primary efficacy outcome of AUC of LNG PK over 8 hours will be calculated using the trapezoidal rule (i.e., noncompartmental technique) as described in [section 11.3](#) below, using all observed data. As women not taking LNG will not have PK samples drawn, and any woman not having complete data to assess 8 hour AUC for any reason will be replaced, these observed data will be per-protocol and will have already excluded women for non-adherence to LNG or other protocol deviations that prevent primary outcome assessment. If participant self-reported short term non-adherence to the other targeted medications (either ARVs or RIF) were such that the PK samples should not have been collected, but were collected in error, then these women will also be replaced, and samples will not be sent for PK testing. Please see [section 11.0](#) of the protocol for more information on the derivation of the primary efficacy outcome.

Each of the two primary objectives will be analyzed as follows. Assessing if increased dose of LNG overcomes DDI with EFV will be assessed by a comparison of randomized Group B to directly assigned Group C. Assessing if increased dose of LNG overcomes DDI with RIF will be assessed by a comparison of directly assigned Group D to directly assigned Group C. Therefore, in each of these primary objectives, the direct assignment Group C (i.e., women on DTG ARV regimen with standard-dose LNG) serves as the control group. Neither of these parallel group comparisons is based on randomization, and thus prior to primary analysis, the distribution of potential baseline confounding factors will be examined between pairwise groups for imbalance. A key factor is race; BMI is not expected to have significant imbalance due to enrollment limits placed on each group for women with BMI  $\geq$  30 kg/m^2.

Descriptive analysis will include the following: a) plots of the concentrations of LNG over time for will be provided to inform the derivation of the primary AUC outcome and other PK parameters (secondary outcomes); b) plots of the summary statistics of concentrations over time by treatment group; c) descriptive statistics of the primary outcome, including mean, standard deviation, median, interquartile range, minimum, and maximum of the primary outcome, will be presented by each study group.

The between group statistic that compares AUC(0-8hr of LNG) is the geometric mean ratio (GMR). The geometric mean and 95% confidence interval about the geometric mean of the primary outcome will be provided by each group. The GMR between Groups B and C (for the EFV objective) and between Groups D and C (for the RIF objective) will be presented. The 90% confidence intervals about the two pairwise GMRs will be compared to the FDA reference standard for bioequivalence in order to determine if LNG AUC is similar between AUC of LNG increased dose versus standard dose in each of the primary objective comparisons. Note that because of the high variability of the PKs of LNG, the bioequivalence interval will be (70%, 143%).

#### 10.6.2 Primary Safety Analysis

Occurrence of the safety outcomes (i.e., number of participants meeting a safety outcome) as defined above will be enumerated and summarized by individual study group. Safety outcomes may be summarized separately by severity grade or type (category or MedDRA grouping) of adverse event.

The secondary objective of comparing safety between standard and increased doses will be achieved by a comparison of the relative number of participants with safety outcome in Groups A+C (or collectively the standard-dose groups) versus the relative number of participants with this outcome in Groups B+D (or collectively the increased dose groups). The statistical hypothesis test for this comparison will be a Fisher's exact test. This comparison may also be repeated as 2 additional pairwise comparisons, especially if analyses of primary objectives

are analyzed separately: (1) randomized Group A versus randomized Group B, which is a randomized comparison and is restricted to HIV+ women taking EFV (2) assigned Group C versus assigned Group D.

Since this study is not powered to compare occurrence of AEs between LNG double dose versus single dose, inference related to comparisons above will focus on describing the magnitude and range of plausible values of observed differences between groups, and will not conclude similarity based on the absence of significant differences by Fisher's exact test.

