### 10.3 Randomization and Stratification

Enrollment to the study is deterministic (not-randomized) for participants who are currently taking either DTG based ART regimens, or RIF-containing anti-TB regimens; these women are directly assigned to Groups C and D, respectively. Participants on EFV-containing ART regimens will be randomized between Groups A (1.5 mg LNG) and B (3.0 mg LNG) in a 1:2 ratio using permuted block randomization that is dynamically balanced within each **institution**. To guard against potential confounding due to body weight or BMI of the participant, enrollment will be **limited** by BMI in the following manner. Women with BMI  $\geq 30$  kg/m^2 will be limited to no more than five within Groups B-D and no more than three within Group A. Therefore, the overall representation of obese women in the study sample will be limited to no more than 15%. The results of either randomization or enrollment to treatment group will be unblinded to participants, and clinical research site staff.

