### 10.6.3 Secondary Outcomes Analysis

The secondary objective of comparing increased dose of LNG EC to standard-dose among women on EFV (randomized comparison), will use analyses parallel to the primary outcome analysis as described above. However, since the hypothesis for this objective is superiority (rather than equivalence), the statistical inference for examination of the confidence interval about the GMR will focus whether this interval includes or excludes 1 (in which a significance difference can be concluded). Conclusions will focus on the estimations and plausible values of the GMR between LNG doses within this EFV comparison. Note this comparison is not subject to confounding because it is randomized comparison. A similar, non-randomized comparison will be performed between randomized Group A and control, directly assigned Group C.

Analyses for other PK parameters of LNG will follow an analysis plan parallel to the primary outcome as described above. Note that derivation of these PK parameter outcomes are according to specifications in [section 11.0](#) below.

Other adverse events (that do not meet the primary safety outcome) and side effects between single dose and double dose may be compared either separately by group, or collapsed over group by LNG dosing (single vs. double).

Further details are outlined in the study's Statistical Analysis Plan (SAP).

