3.2 Secondary Outcome Measures

3.2.1 Safety

Title: Percentage of participants with occurrence of any serious or targeted adverse event (AE) potentially or definitely related to one-time Levonorgestrel administration.

Description: Adverse events were graded according to the Division of AIDS Table for Grading the Severity of Adult and Pediatric Adverse Events (DAIDS AE Grading Table), corrected Version 2.1, July 2017. Relationship of adverse events to study treatment was determined by the study core team and DAIDS clinical representative.

Time Frame: From study entry to day 28

Analysis Population: Participants who received assigned dose of Levonorgestrel

Reporting Groups: A-D

Associated Study Objective: Secondary Objective #4

Details: Occurrence of the safety outcomes (i.e., number of participants meeting a safety outcome) as defined above will be enumerated and summarized by individual study group. Safety outcomes may be summarized separately by severity grade or type (category or MedDRA grouping) of adverse event. From the protocol definition of the safety outcome, the targeted list of reportable AEs includes the following: grade 3 or higher AEs, grade 2 or higher nausea, diarrhea, menorrhagia or metrorrhagia, and ectopic pregnancies.

Inference: Comparison of the relative number (%) of participants with safety outcome who took single-dose LNG versus the relative number of participants with this outcome who took double-dose LNG, will be performed using the safety analysis comparison set as defined below. The statistical hypothesis test for this comparison will be a Fisher's exact test, using a superiority-testing framework. This comparison may also be repeated for the two following pairwise comparisons:

(1) single-dose LNG versus double-dose LNG among HIV+ women taking EFV-based ART

(2) single-dose LNG among HIV+ women taking DTG-based ART versus double-dose LNG among women living with TB taking RIF-containing TB therapy.

Since this study was not powered to compare occurrence of AEs between LNG double-dose versus single-dose, inference related to comparisons above will focus on describing the magnitude and range of plausible values of observed differences between groups, and will **not** conclude similarity based on the absence of significant differences by Fisher's exact test.

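### The planned dose-safety comparison (A+C vs B+D) confounds LNG dose with background drug and disease; the randomised A vs B contrast should be required, not optional

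*Protocol*

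**What the plan says.** Protocol 10.6.2 states how the secondary objective of comparing safety between doses will be met: by comparing the relative number of women with a safety outcome "in Groups A+C (or collectively the standard-dose groups) versus the relative number of participants with this outcome in Groups B+D". It adds: "The statistical hypothesis test for this comparison will be a Fisher's exact test". No stratification or adjustment is given. SAP 3.2.1 repeats the single- versus double-dose Fisher test in a superiority framework and makes it the only formal test planned at interim review.

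The pairwise contrasts are optional in both documents. Protocol 10.6.2: "This comparison may also be repeated as 2 additional pairwise comparisons, especially if analyses of primary objectives" are analysed separately. SAP 3.2.1: "This comparison may also be repeated for the two following pairwise comparisons". One of the two pairs is "randomized Group A versus randomized Group B, which is a randomized comparison and is restricted to HIV+ women taking EFV"; the other is C vs D.

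On allocation of women taking DTG or RIF, Protocol 10.3 says "these women are directly assigned to Groups C and D, respectively". Of the A vs B comparison for PK, Protocol 10.6.3 says: "Note this comparison is not subject to confounding because it is randomized comparison".

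The safety outcome (Protocol 10.2.2) is limited to events judged potentially or definitely related to LNG. On who judges, SAP 3.2.1 says: "Relationship of adverse events to study treatment was determined by the study core team and DAIDS clinical representative".

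**The concern.** Group C differs from Group D in dose, background drug, HIV status and TB status all at once. Together they supply 66 of the 116 women in the pooled test. A difference between the pools can come from DTG versus RIF, or from HIV versus TB, with no dose effect at all. Equally, a real dose effect can be masked.

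The documents accept this principle for PK. Protocol 10.6.1 and SAP 4.1.2 plan checks of baseline imbalance between non-randomised groups, and SAP 4.2.2 plans adjusted geometric mean ratios. No adjustment is planned for safety.

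The protocol's main prompt for running the pairwise contrasts is separate analysis of the two primary objectives. SAP 1.1 now finalises the analysis after the last participant completes, so that prompt may never arise.

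A smaller point concerns attribution. The trial is open-label, and Protocol 10.1 defends this partly by the objectivity of the PK outcome. That argument does not cover a judgement on whether an adverse event was related to LNG.

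**Working it through.** **1. Inputs.** Planned group sizes (Protocol 10.4): A 17, B 33, C 33, D 33. Sum: 17 + 3 × 33 = 116, as stated. The documents give no power or event rate for the safety outcome, so there is no safety figure to reproduce. Every event rate below is an assumption.

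**2. Make-up of the pools.**

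| Pool | n | EFV | DTG | RIF |
|---|---|---|---|---|
| A+C, 1.5 mg | 50 | 17/50 = 34% | 33/50 = 66% | 0% |
| B+D, 3.0 mg | 66 | 33/66 = 50% | 0% | 33/66 = 50% |

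**3. Why stratification does not help.** The DTG stratum has no double-dose women and the RIF stratum has no standard-dose women. Neither allows a comparison of doses within the stratum. Only the EFV stratum does, and that is A vs B.

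**4. Pooled difference with no dose effect.** For background rates pE, pD and pR:

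Double minus standard = (0.50 pE + 0.50 pR) − (0.34 pE + 0.66 pD) = 0.16 pE + 0.50 pR − 0.66 pD.

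The rejection rates come from exact enumeration of Fisher's test at a two-sided 5% level (also assumed).

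| Assumed EFV / DTG / RIF | Pooled difference (points) | Pooled Fisher rejects |
|---|---|---|
| 10 / 10 / 10% | 0 | 3.3% |
| 20 / 10 / 10% | 3.2 + 5.0 − 6.6 = +1.6 | 3.7% |
| 10 / 5 / 20% | 1.6 + 10.0 − 3.3 = +8.3 | 22% |
| 10 / 5 / 30% | 1.6 + 15.0 − 3.3 = +13.3 | 48% |
| 10 / 20 / 5% | 1.6 + 2.5 − 13.2 = −9.1 | 28% |

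The second row shows the effect of the unequal EFV share alone. If attribution to LNG kept all three rates between 1% and 3%, the extremes would be 0.48 + 1.50 − 0.66 = +1.3 and 0.16 + 0.50 − 1.98 = −1.3 points. In the scenarios above, A vs B has an expected difference of zero and Fisher rejects 2.5% (EFV 10%) or 3.4% (EFV 20%) of the time.

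**5. Masking.** Suppose a true +20 points among EFV users (A 10%, B 30%), with C and D both at 25%. Standard pool: (1.70 + 8.25)/50 = 19.9%. Double pool: (9.90 + 8.25)/66 = 27.5%. The pooled difference is +7.6 points.

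**6. Cost in precision.** 95% half-width for a risk difference at an assumed 10% rate in both arms:
- A vs B: 1.96 × √(0.09/17 + 0.09/33) = 17.6 points.
- Pooled: 1.96 × √(0.09/50 + 0.09/66) = 11.0 points.

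Fisher power for 10% vs 30% is 28% for A vs B, against 74% for the pooled test if background rates were equal.

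**7. What is recorded regardless of attribution.** Protocol 7.2 requires recording of grade 2 or higher nausea, diarrhoea, and menorrhagia or metrorrhagia, and of SAEs, with no relatedness condition. Grade 3 or higher AEs are recorded only if considered related to LNG, unless another criterion applies.

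**The case against.** Four points count against the concern.

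- **The plan limits the harm.** Both documents require summaries by individual group, so A and B counts will be visible. Both say the trial is not powered for this comparison, that inference will describe magnitude and plausible range, and that similarity will not be concluded from a non-significant test. This stands as a limit on severity. It deals with low power, however, and a confounded estimate stays confounded however cautiously it is described.
- **A vs B is narrow and imprecise.** It has 50 women, all on EFV, and says nothing about the double dose with RIF, while the safety objective (Protocol 1.3.4) is not specific to EFV. This also stands, and the pooled and C vs D results should still be shown.
- **Detail may lie elsewhere.** The Analysis Implementation Plan, which is not among the documents, may specify an interval method. That would not change the optional status of A vs B.
- **The bias cannot be sized from the documents.** A reader might take the protocol's 14% nausea with DTG and under 4% significant reactions with RIF, assume 5% to 15% for EFV, and infer a bias of −6.4 to −4.8 points in favour of the double dose. The documents do not support that. The DTG figure is stated without grade or LNG attribution, and the RIF figure covers any significant reaction. Women on ART must have had no regimen change for at least 30 days (Protocol 4.1.10), and an AE must be new or worse than baseline (Protocol 7.1). Neither rate measures this outcome.

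A reader might also infer that the whole targeted list could be analysed regardless of attribution. Protocol 7.2 rules that out for grade 3 or higher AEs.

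**Conclusion.** The structural point holds and needs no assumed number: the planned safety contrast is confounded with background drug and disease, stratification cannot repair it, and the one unconfounded contrast is optional. The size and sign of the bias are unknown. The illustrative range of −9.1 to +13.3 points rests entirely on assumed rates, and shrinks to about ±1.3 points if attribution to LNG leaves background rates of 1% to 3%. The documents do not show that the double dose would be favoured or disfavoured, and they already decline to claim similarity. This is a cheap improvement to a secondary, descriptive analysis and does not touch the primary PK objectives.

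**What to change.** In Protocol 10.6.2 and SAP 3.2.1:

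1. Change the randomised A vs B comparison from optional to required. Report it as a risk difference with a 95% CI, named as the unconfounded dose-safety estimate and stated to apply to women on EFV.
2. Keep A+C vs B+D and C vs D as descriptive results, each labelled as confounded with background therapy. Carry the same label into the interim safety report.
3. Keep the protocol-defined LNG-related outcome. Add a supportive analysis regardless of attribution, limited to events recorded that way: grade 2 or higher nausea, diarrhoea, menorrhagia or metrorrhagia, and SAEs.

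The cost is wording and a small amount of extra tabulation, with no new data collection. The statistical price is precision: 50 women instead of 116, or about 17.6 against 11.0 points half-width at an assumed 10% rate. A vs B should therefore be read as an estimate with its interval and not as a powered test.

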### 10.6.3 Secondary Outcomes Analysis

The secondary objective of comparing increased dose of LNG EC to standard-dose among women on EFV (randomized comparison), will use analyses parallel to the primary outcome analysis as described above. However, since the hypothesis for this objective is superiority (rather than equivalence), the statistical inference for examination of the confidence interval about the GMR will focus whether this interval includes or excludes 1 (in which a significance difference can be concluded). Conclusions will focus on the estimations and plausible values of the GMR between LNG doses within this EFV comparison. Note this comparison is not subject to confounding because it is randomized comparison. A similar, non-randomized comparison will be performed between randomized Group A and control, directly assigned Group C.

Analyses for other PK parameters of LNG will follow an analysis plan parallel to the primary outcome as described above. Note that derivation of these PK parameter outcomes are according to specifications in [section 11.0](#) below.

Other adverse events (that do not meet the primary safety outcome) and side effects between single dose and double dose may be compared either separately by group, or collapsed over group by LNG dosing (single vs. double).

Further details are outlined in the study's Statistical Analysis Plan (SAP).

### 10.6.4 Exploratory Outcomes Analysis

All host genotypes will be treated as ordinal variables (as 3 levels for individual SNPs, and either 3 or 12 levels for composite *CYP2B6/CYP2A6* genotypes). For each SNP or genotype, associations with PK concentrations with the AUC of LNG will be evaluated. The primary focus will be on SNPs/genotypes with very strong *a priori* evidence for effect on drug exposure (i.e., *CYP2B6/CYP2A6* SNPs for efavirenz, *UGT1A1* for dolutegravir). For example, we will explore whether *CYP2B6/CYP2A6* genotypes that are known to predict higher plasma efavirenz concentrations are also associated with lower levonorgestrel concentrations.

Side effects, tolerance, and acceptability of LNG will be summarized across participants grouped by LNG dose.

Further details are outlined in the study's Exploratory Statistical Analysis Plan.

## 11.0 PHARMACOLOGY PLAN

### 11.1 Pharmacology Objectives

See [section 1.0](#) for study objectives.

### 11.2 Pharmacology Study Design

This is a pharmacology study, thus, the pharmacology study design is specified in the overall study design described in [section 6.3.9](#).

### 11.3 Primary and Secondary Data, Modeling, and Data Analysis

#### LNG analysis

The PK parameters for LNG include: maximum concentration ( $C_{max}$ ), time to maximum concentration ( $T_{max}$ ), minimum concentration ( $C_{min}$ ), **time to minimum concentration ( $T_{min}$ )**, oral clearance (CL/F), volume of distribution (Vd), elimination half-life ( $T_{1/2}$ ), and area under the concentration-time curve over 8 hours ( $AUC_{0-8h}$ ), 24 hours ( $AUC_{0-24h}$ ), 48 hours ( $AUC_{0-48h}$ ), and to infinity ( $AUC_{inf}$ ). Standard noncompartmental techniques will be used to determine these PK parameters using the software package Phoenix WinNonLin (Certara®). The AUC (including the primary outcome) will use the linear up/log down version of the trapezoidal rule. This version of the trapezoidal rule uses linear interpolation between untransformed data up to  $C_{max}$ , and between log-transformed data from  $C_{max}$  through  $C_{last}$  [81, 82].  $C_{max}$  will be taken as the maximum observed concentration.  $T_{max}$  is the time at which  $C_{max}$  occurs.  $C_{min}$  will be taken as the minimum observed concentration after the observed dose. Apparent oral clearance will be calculated as  $CL/F = \text{dose}/AUC_{0-24}$  or  $CL/F = \text{dose}/AUC_{0-48}$ . The  $T_{1/2}$  will be determined using regression analysis when possible.

